## **B. Donor Screening** (check all that apply)

- Donor Selection
  - Donor screening Questionnaire (see Supplement 2)
    - AABB DHQ or AABB DHQ modified/derived
    - Other
  - Donor interview
    - Physician
    - Nurse Practitioner
    - Physician Assistant
    - Nurse
    - Research coordinator or assistant
  - Donor physical examination
    - Physician
    - Nurse
    - Research coordinator or assistant
    - Research Nurse
- Laboratory

- No laboratory screening done
- Screening laboratories unknown (FMT product)
- Stool
  - Clostridium difficile toxin by PCR
  - *C. difficile* toxin EIA
  - *C. difficile* culture (anaerobic culture for toxigenic *C. difficile*)
  - Direct stool cytotoxin with tissue culture
  - *C. difficile* by glutamate dehydrogenase (GDH) testing
  - Routine bacterial culture for enteric pathogens (E coli, Salmonella, Shigella, Yersinia, Campylobacter)
  - Culture for *Listeria monocytogenes*
  - Culture for Vibrio (parahaemolyticus and cholerae)
  - Fecal Giardia antigen or DFA
  - Fecal Cryptosporidium antigen or DFA
  - Acid-fast stain for Cyclospora and Isospora
  - Trichrome Ova and parasites exam (O&P)
  - Rotavirus via EIA
  - Norovirus PCR
  - VRE culture
  - MRSA
  - New Delhi-Metallo-beta-lactamase-1 (NDM-1)
  - Carbapenem-resistant Enterobacteriaceae
  - *Helicobacter pylori* fecal antigen
  - Adenovirus EIA
  - Fecal calprotectin
  - Fecal lactoferrin
  - Luminex xTAG® Gastrointestinal Pathogen Panel (xTAG GPP)
  - BioCode GI panel
  - RIDA®GENE Bacterial Stool Panel
  - FilmArray® GI Panel
  - Other\_\_\_\_
- Serology
  - Norovirus
  - Helicobacter pylori serology (IgG, IgM or IgA)
  - JC Virus Ab
  - Strongyloides stercoralis Ab (IgG)
  - Schistosoma Ab (IgG)
  - Entamoeba histolytica Ab (IgG)
  - HIV, type 1 and 2 (Ab)
  - HIV, type 1 & 2 (qualitative PCR)
  - HIV p24 Ag test
  - HAV total Ab
  - HAV IgM
  - HBsAg
  - HBsAb
  - anti-HBc (IgG and IgM)
  - HCV Ab
  - RPR
  - Syphilis (TP) Ab test
  - FTA-ABS

- EBV Ab panel
- EBV PCR
- CMV IgG
- CMV PCR
- HSV 1 & 2 IgG
- Human T cell lymphoma virus 1 & 2
- Trypanosoma antibody
- Other

## C. Recipient Screening

- Site specific exclusion criteria (check if site protocol excludes patients with any of the following)
  - Age <\_\_

  - o Age >\_\_
  - o BMI
  - Medical conditions
    - List conditions
  - o Pregnancy/lactation
  - o Recent or ongoing antibiotic use
  - Allergy
  - Malignancy
  - o Immunosuppression
  - o Other\_\_\_
- Laboratory (baseline screening of recipient)-check any which apply
  - o HIV 1 & 2
  - o Hepatitis A
  - o Hepatitis B surface Ag
  - o Hepatitis B surface Ab
  - Hepatitis B core Ab
  - o Hepatitis C Ab
  - o RPR
  - Other

## **D.** Transplant material preparation

- Location of material preparation
  - o Laboratory (research)
  - o Laboratory (clinical)
  - o Endoscopy unit
  - o Pharmacy
  - o Clinic/office
  - Other Patient care area (hospital room, infusion center)
- Approximate weight (grams) or volume (mL) of stool used in preparation
- Diluents
  - o None/NA
  - Water
    - Volume\_\_\_
  - Saline
    - Volume\_\_\_
  - Glycerol
    - Percent\_\_\_
  - o Other

- Processing
  - o Blender
    - Household
    - Commercial
    - Laboratory mixer
  - Manual mixing
- Filtration
  - o None
  - o Coffee filter
  - o Medical gauze
  - o Metal/disposable sieve
  - o Laboratory microfilter
- Material Storage
  - o Stool
    - Fresh (used within \_\_\_hours of passage)
    - Frozen stool (used within \_\_\_months)
      - -20°C
      - ≤-70°C
  - Other material (specify Openbiome, SER-109, RBX2660, etc.)
    - Room temperature
    - Refrigerated
    - Frozen
- Amount of material delivered
  - o Volume (ml)
  - Number of capsules
  - o Contents/dose (CFU) if non-stool product

## E. Method of delivery

- Oral ingestion: capsule
  - o Fresh capsule
  - o Frozen capsule
  - o Lyophilized capsule
  - o Number of capsules used
- Oral ingestion: liquid
- Nasogastric tube
- Naso-intestinal tube
- Upper endoscopy
- Sigmoidoscopy
- Colonoscopy
- Enema

#### F. Delivery schedule

- Single dose delivery/ingestion
- Multiple dose
  - Number of doses\_\_\_\_
  - Dosing Schedule
    - Daily
    - > Weekly
    - o Monthly
- Maintenance (chronic therapy)
  - Schedule

## **Supplement 2. FMT Donor Questionnaire Data Elements**

Are you:		
1. Feeling healthy and well today?	Yes	No
2. Currently taking any medication for infection?	Yes	No
Have you:		
3. Taken any antibiotics within the past 6 months?	Yes	No
4. Had any fevers, vomiting, diarrhea or other symptoms of infection within the past	4 weeks?	
	Yes	No
In the past 8 weeks have you		
5. Had any vaccinations or other shots?	Yes	No
6. Had contact with someone who has had the Smallpox vaccine?	Yes	No
In the past 12 months have you:		
7. Had a blood transfusion?	Yes	No
8. Had a transplant (organ, tissue, bone marrow, dura mater- brain covering)?	Yes	No
9. Had a skin or bone graft?	Yes	No
10. Come into contact with someone else's blood?	Yes	No
11. Had an accidental needle stick?	Yes	No
12. Had sexual contact with anyone who has HIV/AIDS?	Yes	No
13. Had sexual contact with a prostitute or anyone else who takes money or drugs as	s payment f	or
sex?	Yes	No
14. Had sexual contact with anyone who has ever used needles to take drugs or stere	oids, or	
anything NOT prescribed by their doctor?	Yes	No
15. Had sexual contact with anyone who has hemophilia or has used clotting factor of	concentrate	s?
	Yes	No
16. Female donors: Had sexual contact with a male who has ever had sexual contact	with anothe	r
male (male donors circle "I am male)?	Yes	No
	I am male	
17. Had sexual contact with a person who has hepatitis?	Yes	No
18. Lived with a person who has hepatitis?	Yes	No
19. Had a tattoo?	Yes	No
20. Had an ear or body piercing?	Yes	No
21. Been treated for syphilis or gonorrhea?	Yes	No
22. Been in lockup, jail or prison for >72 hours?	Yes	No
In the past three years have you		
23. Been outside the United States or Canada?	Yes	No
List location/time spent:		
From 1980 through 1996,		
24. Did you spend time that adds up to three (3) months or more in the United Kingo	dom? Yes	No

25. Were you	a member of the U.S. military, a civilian military employee or a depend	dent mem	ber of
the U.S. milita		Yes	No
From 1980 to	the present,		
26. Did you sp	end time that adds up to five (5) or more years in Europe?	Yes	No
27 Receive a	blood transfusion in the United Kingdom or France?	Yes	No
From 1977 to	the present, have you		
28. Received r	noney, drugs, or other payment for sex?	Yes	No
29. Male dono	rs: had sexual contact with another male, even once (female donors c	ircle "I am	
female")?		Yes	No
		I am fem	ıale
Have you EVE	R		
30. tested pos	itive for HIV/AIDS virus?	Yes	No
31. used need	les to take drugs or steroids or anything NOT prescribed by your doct	or? Yes	No
32. used clotting factor concentrates?		Yes	No
33. had viral hepatitis?			No
34. had any type of cancer (including leukemia)?		Yes	No
35. had sexual contact with anyone who was born or lived in Africa?		Yes	No
36. been in Africa?		Yes	No
37. had sex for drugs or money?		Yes	No
38. had any of	the following gastrointestinal diseasesor problems?		
a.	Irritable bowel syndrome?	Yes	No
b.	Crohn's disease?	Yes	No
C.	Ulcerative Colitis?	Yes	No
d.	Chronic diarrhea?	Yes	No
e.	Gastrointestinal cancers?	Yes	No
f.	Celiac disease?	Yes	No
39. received g	rowth hormone made from human Pituitary glands?	Yes	No
40. Have any o	of your relatives had Creutzfeldt-Jakob disease?	Yes	No
General Medic	cal History		
	ve any autoimmune diseases (for example: Rheumatoid arthritis, Mul	tiple Scler	osis,
Lupus)		Yes	No
If yes, please l	ist:		
	ve any neurologic diseases (for example: Parkinson's, Autism, ALS)?	Yes	No
If yes, please l	ist:		

# **Supplement 3. FMT Treatment Indications and Baseline Donor/Recipient Characteristics**

#### A. FMT Indication

- C. difficile
  - Refractory
  - o Recurrent
  - Severe
- Inflammatory Bowel Disease
  - Ulcerative colitis
  - o Crohn's disease
  - o IBD-U
  - o Pouchitis
- Irritable bowel syndrome
  - o IBS-D
  - o IBS-C
  - IBS-M
  - o Other functional disorder
- Chronic constipation
- Obesity
- Diabetes
- Metabolic syndrome
- NAFLD/NASH
- Neurologic or Neurodevelopmental disorder
- Other

## B. Baseline Characteristics

- Donor (if known)
  - o Age
  - o Race/Ethnicity
  - o Gender
  - o Height
  - Weight
  - Donor medical conditions (check any which apply)
    - No significant medical or surgical history
    - BMI ≥30
    - Hypertension
    - Hyperlipidemia
    - Diabetes type II
    - Depression/anxiety
    - CAD
    - Cerebrovascular disease
    - Asthma
    - Other\_\_\_
- Recipient characteristics (baseline)
  - o Age
  - o Race/Ethnicity
  - Gender

- Height
- Weight
- Medical co-morbidities
  - Metabolic (hypertension, diabetes II, hyperlipidemia)
  - Autoimmune (hypothyroid, RA, SLE)
  - Asthma/Allergic-Atopic conditions
  - Cardiovascular
  - Neurological conditions (MS, Parkinson, Alzheimer's, autism)
  - Psychological (depression, anxiety, eating disorder)
  - IBS
  - IBD
  - Immunocompromised from medical condition or medication
  - Other
- Labs (glucose, cholesterol, HDL, LDL, triglycerides, ALT, alkaline phosphatase, bilirubin, albumin, BUN, creatinine)
- CDI baseline characteristics
  - Disease characteristics (pre-FMT)
    - Mild illness (recurrent)
    - Moderate (more severe but uncomplicated disease)
    - Severe
    - Severe complicated
  - Duration of *C. difficile* infection (weeks between initial diagnosis and FMT)
  - Number of CDI episodes
  - C. difficile strain
    - o Nap-1
    - Non Nap-A
    - o Unknown
  - Other treatments courses received (and number of courses of each, if known) for CDI prior to FMT
    - o Metronidazole
    - o Vancomycyin
    - o Vancomycin taper/pulse dose
    - o Fidaxomicin
    - o Nitazoxanide
    - o Rifaximin
    - o IVIG
    - o Saccharomyces. boulardii
    - o Lactobacillus GG
    - Other probiotic
    - o Other\_\_
  - Immediate Pre-FMT treatment(s)
    - Antisecretory therapy?
      - No
      - Yes
- H2 blocker
- Proton Pump inhibotor
- o Probiotics?
  - No
  - Yes

- list
- Antibiotics?
  - No
  - Yes
- Metronidazole
- Vancomycin
- Other
- o If yes, were antibiotics stopped? (yes/no)
- Number of days off antibiotics prior to FMT
- IBD Baseline characteristics
  - o Type of IBD
    - CD
    - UC
    - IBD-U
    - Pouchitis
  - Disease location/extent
    - Montreal classification for adults >18 y/o
    - Paris classification for children <18 y/o

  - IBD treatment pre-FMT
    - Antibiotics
      - IV
      - Oral
    - Probiotics
    - Diet
      - Type of diet
    - Mesalamine
      - Oral
      - Rectal
    - Thiopurines
    - Methotrexate
    - Steroids
      - Oral
      - Rectal
      - IV
    - Biologics
      - Anti-TNF
      - Anti-Integrin
      - Ustekinumab
      - Other
    - Cyclosporin or tacrolimus
    - Other
  - IBD history
    - Number of years since initial diagnosis
    - Bowel surgery (ever)
    - IBD-related hospitalizations (within 12 months prior to FMT)
  - Severity of IBD at time of FMT (quiescent, mild, moderate, severe)
  - Disease activity scores (if available)

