Despite the importance of the gut microbiota in maintaining the health of the host, growing evidence suggests that it may also be an important factor in the pathogenesis of a variety of diseases, particularly those that have shown a rapid increase in incidence over the past few decades. These include type 1 and type 2 diabetes mellitus, atherosclerosis, asthma, colon cancer, inflammatory bowel disease (IBD), and autism^10. Advances in genomic technology, principally DNA sequencing and SNP mapping used for genome-wide association studies, combined with biocomputational algorithms, have revealed the host genetic underpinnings of these complex disease processes. In most circumstances, the contribution of host genetics to disease development is well under 50%, implicating the importance of environmental influences. The observation that these diseases have shown a steadily increasing incidence over the past several decades, the geographic distribution of disease clustering in industrialized nations, and immigration studies revealing the adoption of disease risk of the host country within 1 or 2 generations, emphasize the importance of environment in the pathogenesis of these diseases. The notion that an alteration in the composition of the gut microbiota as a possible etiologic factor in the predisposition to immunologically-mediated disease has been proposed as one of the environmental factors that may play a role in the increasing incidence of the diseases associated with the gut microbiota mentioned previously.

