## 8.3 Statistical Methods

The registry will be designed in a manner that will facilitate statistical analyses for the purpose of signal detection, generation of descriptive data, and the conduct of comparative effectiveness studies. There will be several major advantages of the registry design as opposed to a system of spontaneous reporting. Most importantly, a prospective cohort of patients who undergo FMT with collection of predefined outcomes will allow accurate estimation of incidence rates. In contrast, systems that rely on spontaneous reporting have incomplete numerator data and lack denominator data. The ability to calculate incidence rates greatly facilitates both descriptive epidemiology and signal detection.

As noted above, registries are used to provide precise estimates of outcomes in real-world practice and document that potential adverse events occur at less than a pre-specified incidence with a predefined level of confidence. Thus, descriptive statistics with 95% confidence intervals will be determined for the safety and effectiveness outcomes to provide precise estimates of incidences. As mentioned above, if an adverse event does not occur in the planned population of 4,000 patients, we will have 95% confidence that the adverse event occurs at a rate of less than one in a thousand patients undergoing FMT.

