To increase our ability to study unanticipated adverse events, we will include a retrospective control group of patients with recurrent CDI identified from insurance claims using Optum Insight Life Sciences, Inc data. Using these data, we can determine the incidence of relevant outcomes in a group of patients with recurrent CDI treated with antibiotics rather than FMT. The incidence of relevant outcomes in this group can be compared to the patients treated with FMT in the registry. To assure the feasibility of this approach, we have conducted a preliminary analysis of these data to identify the number of patients who will be included in the control cohort. Recurrent CDI was defined as having a physician-made diagnosis of CDI (ICD-9 008.45) treated with 3 separate courses of antibiotics with metronidazole, vancomycin, or fidaxomicin (at least one of which were vancomycin or fidaxomicin). The 3 antibiotic prescriptions had to be at least 10 days apart and the third course needed to be started within the 90 days following the CDI diagnosis. We identified 4,313 patients meeting this definition with mean follow-up of 1.70 years. The sample size should be sufficient to address questions on relatively rare outcomes. For example, at age 68 years (the median age in our control cohort), the probability of death in the next 12 months is 1.75% and the expected survival is 18.8 years (CDC lifetables). With an average follow-up time of 1.70 years, assuming equal number of subjects undergoing FMT and equal follow-up time, we would have 90% power to detect a hazard ratio of 0.77 for a difference in survival rates between FMT and antibiotic treated patients.

As mentioned above, the FMT registry also will support comparative effectiveness studies focusing on different methods of delivery of FMT. Comparative effectiveness studies rely on the ability to adequately account for differences between the treatment groups. The FMT registry will facilitate this by collecting robust data on the indications for therapy and other covariates that describe the recipients and the methods of delivery. Such data will support standard statistical methods including logistic, Cox, and other regression methods, and the development of propensity scores and risk scores for risk adjustment.

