## Supplement 6. FMT Long-term Adverse Outcomes (up to 2 years by physician report and 10 years by patient report)

- Characteristics
  - Height
  - Weight
- Serious Infection (HIV, viral hepatitis, prion, etc)
  - *Use of new drugs* 
    - o Describe
  - Surgeries or other Procedures
    - Describe
- Diagnosis of any new condition
  - o Autoimmune (hypothyroid, ITP, RA, SLE, MS, celiac, Type I diabetes, Sjogrens)
  - o Asthma
  - Allergy/atopy
  - Metabolic disease
    - Diabetes II
    - Obesity
  - o Psychiatric disorder
  - Neurologic disease
    - Parkinson's disease
    - Amyotrophic lateral sclerosis (ALS)
    - Autism spectrum diagnosis
  - Cardiovascular disease
    - Myocardial infarction
    - Coronary artery revascularization
    - Cerebrovascular accident
    - Hypertension
  - o Colon cancer
  - Other malignancy
  - Inflammatory bowel disease
    - Crohn's
    - Ulcerative colitis
    - IBD-U
  - o IBS
- IBS-C
- IBS-D
- IBS-M
- o Other
- Hospitalization
  - o Reason for hospitalization
  - o FMT related (related, possibly related, unrelated)
- Life-threatening illness
  - o Describe/diagnosis
  - o FMT related (related, possibly related, unrelated)
- Death
  - Cause of death
  - o FMT related (related, possibly related, unrelated)

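### Supplement 6 counts colon cancer and other malignancy as new long-term diagnoses, but the recipient baseline list in Supplement 3B has no prompted item for prior or current cancer

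*Protocol*

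**What the plan says.** Supplement 6 sets out the long-term adverse outcomes, reported by physicians to 2 years and by patients to 10 years. Under "Diagnosis of any new condition" it lists colon cancer and "Other malignancy".

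Supplement 3B lists the recipient's baseline co-morbidities: metabolic, autoimmune, asthma/allergic, cardiovascular, neurological, psychological, IBS, IBD, "Immunocompromised from medical condition or medication" and Other. It has no cancer item.

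Malignancy or cancer history appears in two other places:
- Supplement 1C has it under "Site specific exclusion criteria (check if site protocol excludes patients with any of the following". Supplement 1 is completed once per site, at initiation.
- Supplement 2, question 34, asks about any cancer, but it is put to donors.

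Section 4.2 excludes only incarcerated persons, so recipients with past or current cancer can enrol. Section 5.1 describes the contents of Supplements 1-6 as elements that may be collected.

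On use of the data, section 8.3 says that a prospective cohort "with collection of predefined outcomes will allow accurate estimation of incidence rates". Of the claims-based control group it says: "The incidence of relevant outcomes in this group can be compared to the patients treated with FMT in the registry".

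**The concern.** A diagnosis can be called new only against a known starting state. Supplement 3B supplies a starting state for nearly every other disease group in Supplement 6, but not for cancer, which looks like an oversight.

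Long-term safety is the primary objective (section 2.1). Section 1.2 names "atherosclerosis, asthma, colon cancer, inflammatory bowel disease (IBD), and autism" among the diseases in which the gut microbiota may be a factor, so cancer is an outcome the registry has reason to study.

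Two things are at stake. A cancer reported at, say, year 6 by a patient through the portal may be a first cancer or the return of an old one, and no named baseline item tells them apart. Also, an analyst who wants to restrict to patients without prior cancer, or to adjust for it, has no reliable variable to do so, either within the registry or in a comparison with the claims-based group. An analysis plan can define a denominator, but it cannot create a baseline variable that was not collected.

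**Working it through.** **1. The protocol's own figures (section 8.1).** For 200 events in 4,000 (5.0%), the Wilson 95% interval is 4.37% to 5.72%, which matches the stated 4.4% to 5.7%. For 0 events in 4,000, the one-sided 95% upper bound is 1 − 0.05^(1/4000) = 0.00075 and the two-sided bound is 1 − 0.025^(1/4000) = 0.00092. Both are below the stated 1 in 1,000. The figures reproduce.

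**2. Size of a possible distortion.** The protocol gives neither a prior-cancer prevalence nor a cancer incidence, so the inputs here are assumptions:
- f, share of recipients with prior cancer: 5%, 10%, 20%
- p, true first-cancer incidence in the rest: 2.0%
- r, share of those with prior cancer for whom an old cancer is recorded as new: 0 or 5%

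Dividing by all 4,000, apparent incidence = (1 − f)·p + f·r.

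| f | with history | first cancers in the rest | r = 0 | r = 5% |
|---|---|---|---|---|
| 5% | 200 | 2.0% × 3,800 = 76 | 76/4,000 = 1.9% | (76 + 10)/4,000 = 2.15% |
| 10% | 400 | 2.0% × 3,600 = 72 | 72/4,000 = 1.8% | (72 + 20)/4,000 = 2.3% |
| 20% | 800 | 2.0% × 3,200 = 64 | 64/4,000 = 1.6% | (64 + 40)/4,000 = 2.6% |

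The apparent figure equals p exactly when r = p. At f = 10% that is 2% of 400, or 8 patients. Below this it is too low and above it too high. Nothing in the named items shows on which side the registry lies.

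**3. Against sampling error.** At 2.0% with n = 4,000 the Wilson 95% interval is about 1.61% to 2.48%. The values at f = 5% and 10% (1.8% to 2.3%) lie inside it. Only the values at f = 20% (1.6% and 2.6%) fall just outside.

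**4. Limits of this calculation.** It gives patients with any prior cancer no chance of a genuine new one. In fact a patient with an earlier cancer at another site can still develop a new colon cancer or a new, different malignancy. The r = 0 column is therefore an extreme. For colon cancer only prior colon cancer is prevalent disease. The relevant f is then a subset of the assumed range, and the dilution factor 1 − f is closer to 1.

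**5. Effect of a smaller denominator on the zero-event bound.** With 10% removed (n = 3,600) the one-sided bound is 1 − 0.05^(1/3600) = 0.00083. With 20% removed (n = 3,200) it is 0.00094. Both remain below 0.001. The two-sided bound at n = 3,600 is 0.00102.

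**The case against.** The case for leaving the list alone has several parts.

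- **The list is indicative.** Section 5.1 speaks of elements that may be collected, and the eCRF is not shown. This stands, and it limits the point to the list as specified.
- **Other could hold a cancer history.** It could, but nothing prompts for it, and a blank entry does not establish absence.
- **Supplement 6 already asks for new conditions.** This gives partial protection against counting old disease, chiefly while sites report at 1 month, 6 months, 1 year and 2 years. It leaves the judgement to the patient afterwards, and it does not identify who had cancer at entry. The 5% misrecording rate used above has no basis in the documents.
- **Patients are contacted at least annually, so history could be asked later.** True, with the limits of recall. That too would need an item to be added.
- **The claims-based group was introduced for unanticipated events.** Section 8.3 works its example on death, with mean follow-up of 1.70 years, and names no cancer comparison. The point applies only if one is made.

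A reader might go further and infer that the 4,000 denominator, or the bound of 1 in 1,000, is wrong. The documents do not support that. Section 8.1 states its bound per patient undergoing FMT, and events over all treated patients is a legitimate estimand.

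A reader might also infer that the coarse lines, such as "Asthma/Allergic-Atopic conditions" or the single cardiovascular line, are the same defect. They are not: recipients without the group tick are still a valid at-risk set. Suppose 10% have the specific condition and 30% carry the tick. Then 2,800 rather than 3,600 are usable, and the 95% interval around 5.0% is 4.25-5.87% rather than 4.33-5.76%, about 0.1 percentage point per limit. Splitting those lines would be preference.

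**Conclusion.** The point holds, limited to the two cancer outcomes. As specified, the recipient baseline list has no prompted cancer item, and neither the site-level policy box nor the donor questionnaire fills the gap. Recurrent or pre-existing cancer cannot be reliably told from new cancer, and prior cancer is not reliably available for restriction or adjustment.

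The effect cannot be sized from the documents. The scenarios suggest a modest shift of uncertain direction, but they rest wholly on assumed prevalence, incidence and misrecording. What gives the point its weight is that the information belongs to baseline and serves the primary objective.

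**What to change.** Add two patient-level items to the recipient list in Supplement 3B: prior or current colon cancer, and other prior or current malignancy with its type. If the eCRF already records these, say so in Supplement 3B instead. The choice of denominator, all treated patients or those without the cancer in question at baseline, can be left to the SAP.

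The cost is two extra baseline entries per recipient, with no added visits or tests.

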#### 4.1.1 Recipient Inclusion Criteria

- Ability to give informed consent
- Receiving FMT or other gut-related microbiota product within 90 days after providing consent
- Access to internet and/or [contact] Donor Inclusion

- Ability to give informed consent
- Providing stool sample for FMT

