## **Supplement 4. FMT Effectiveness Outcomes**

## A. Clostridium Difficile Infection

- Post-FMT treatment(s)
  - o Probiotics?
    - No
    - Yes
      - list
  - Antibiotics?
    - No
    - Yes
      - Metronidazole
      - Vancomycin
      - Fidaxomicin
      - Other
  - Days post-FMT antibiotic stopped
- Cure (Resolution of diarrhea without need for further anti-CDI therapy)
  - Cured with single FMT
  - Cured with >1 FMT
- Failure/Recurrence
  - o How recurrence was diagnosed
    - Symptoms only
    - Stool testing only
    - Symptoms and +stool testing (EIA)
    - Symptoms and + stool testing (PCR)
  - Time of recurrence (weeks post-FMT)
- Antibiotics received post-FMT for treatment of other infections
  - Agent
  - o Indication
  - Months post-FMT

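### The method of CDI diagnosis is recorded for a recurrence after FMT but not for the infection that led to FMT, so patients without test-confirmed CDI may enter the cure rate and be only partly identifiable

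*Protocol*

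**What the plan says.** **After FMT.** Supplement 4, part A, has an item "How recurrence was diagnosed". It offers symptoms only, stool testing only, and symptoms with a positive test, where EIA ("Symptoms and +stool testing (EIA") and PCR are separate options. The same list defines cure by symptoms and treatment, with no stool test: "Cure (Resolution of diarrhea without need for further anti-CDI therapy".

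**Before FMT.** The CDI block in Supplement 3, part B, lists severity, duration ("weeks between initial diagnosis and FMT"), "Number of CDI episodes", "C. difficile strain", earlier treatment courses and treatment immediately before FMT. It has no item for the method, result or date of the diagnosis that led to FMT.

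**Elsewhere.**
- The indication list in Supplement 3, part A, divides C. difficile only into refractory, recurrent and severe.
- The recipient tests in Supplement 1, part C ("Laboratory (baseline screening of recipient)-check any which apply"), are HIV, hepatitis A, B and C, RPR and an open field. The C. difficile stool tests in Supplement 1, part B, are for donors.
- Section 4.1.1 asks for consent, an access requirement and "Receiving FMT or other gut-related microbiota product within 90 days after providing consent". It does not ask for confirmed CDI.
- Section 5.1 refers to Supplements 1 to 6 for the data elements and to no other list.

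**The concern.** By separating symptoms-only, test-only, EIA and PCR recurrences, the plan treats these as different kinds of evidence. It applies that distinction after FMT but not before.

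The gap matters because of how cure is defined. If a recipient is treated as having CDI without confirmation and the diarrhea has another cause, whether it resolves says little about the effect of FMT on CDI. The baseline list itself includes IBS and IBD, two other possible causes, as recipient co-morbidities.

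Two uses of the data are exposed. Section 8.3 promises effectiveness outcomes with 95% confidence intervals. It also promises comparisons of delivery methods, adjusted using data on indication and other covariates. If diagnostic practice differs between sites, and so perhaps between routes or products, part of an observed difference in cure could reflect who was labelled as having CDI. A later analysis plan cannot adjust for a field that was never collected.

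**Working it through.** **1. Is the field missing everywhere?** The lists were set side by side.

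| Place | Method of CDI diagnosis in the recipient |
|---|---|
| 4.1.1, recipient eligibility | not required |
| Supplement 1C, recipient screening | not listed |
| Supplement 3A, indication | not listed |
| Supplement 3B, CDI baseline | not listed |
| Supplement 4A, recurrence | listed, four options |

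The protocol states no figure on this point, so there is nothing to reproduce.

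**2. What could stand in for it?**
- *Strain.* A known strain implies a laboratory finding. The unknown category mixes tested with untested patients, so it does not isolate the unconfirmed.
- *IBS or IBD co-morbidity.* This marks patients with a possible other cause of diarrhea but says nothing about testing.
- *Biorepository stool.* Section 5.2 and Appendix A plan a recipient sample before FMT for at least 1,000 procedures, against 4,000 registry patients. The sample is intended for microbiome analysis and is not described as a diagnostic test.

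These allow partial identification only.

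**3. How large could the effect be?** Let f be the share of CDI-labelled recipients without true CDI and c the share of them whose diarrhea resolves. The documents give neither. Take 89%, the mean cure rate in section 1.2, as the rate in true CDI. This too is an assumption, because that section does not say how CDI was diagnosed in the reports behind it.

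Observed cure = 0.89 × (1 − f) + c × f.

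With f = 10%:
- c = 30%: 0.801 + 0.030 = 83.1%, a shift of −5.9 points
- c = 50%: 0.801 + 0.050 = 85.1%, −3.9 points
- c = 70%: 0.801 + 0.070 = 87.1%, −1.9 points
- c = 100%: 0.801 + 0.100 = 90.1%, +1.1 points

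The shift equals f × (c − 0.89), so its sign changes at c = 89%. With c from 30% to 100%, f = 5% gives 86.1% to 89.6% and f = 20% gives 77.2% to 91.2%.

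**4. Against sampling error.** The 95% half-width at 89% is 1.96 × √(0.89 × 0.11 / n): 1.9 points at n = 1,000, 1.4 at 2,000 and 1.0 at 4,000. The last applies only if all 4,000 registry patients have CDI. The registry takes every indication, so the half-width for CDI cure will be wider than that.

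**5. In a comparison.** Suppose two routes have the same true cure rate of 89% but unconfirmed shares of 5% and 10%. They would appear to differ by (0.10 − 0.05) × (0.89 − c). That is 3.0 points at c = 30%, 2.0 points at c = 50%, and 0.6 points the other way at c = 100%. With equal shares and equal c, no spurious difference arises; a real difference shrinks by the factor 1 − f.

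**The case against.** **No document shows that unconfirmed patients are enrolled.** A reader might infer from the missing field that they are. The documents support only that confirmation is neither required nor recorded. Sections 1.2 and 1.3 describe FMT use in CDI that has not responded to standard therapy, which makes an unsupported diagnosis less likely but does not exclude it. This objection stands.

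**CDI cure is not the main result.** A reader might treat it so. Section 2.1 makes safety primary and lists effectiveness as a secondary objective to be characterized. This stands and limits the importance of the point.

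**The bias need not be downward.** Assuming low resolution in unconfirmed patients gives only downward shifts. Section 3 of the working above shows that the sign depends on an unknown. This stands.

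**Some adjustment is possible without the item.** IBS, IBD, strain and the stool subset are available, so it would be wrong to say that nothing can be done later. This stands in part: the proxies do not identify who was tested or how.

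**The item does not catch every misclassification.** A patient with a positive test whose diarrhea comes from IBS or IBD would count as symptoms plus a positive test. This stands and shapes the fix.

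**All-comers is the right target for a real-world registry.** This stands. It is a reason against making the test-confirmed rate primary, but not against recording the item.

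**Differential bias needs differential diagnosis.** Section 6.1 reports wide variation in FMT practice between sites but says nothing of diagnostic practice by route or product. The effect on comparisons is therefore conditional.

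**The supplements show elements that may be collected, and the eCRF is not shown.** The final form could contain the item. The protocol points to no other list, however, so the gap stands in the document as written.

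**Conclusion.** The asymmetry is real. The diagnostic basis is recorded for a recurrence and not for the infection that led to FMT, and no other listed element supplies it. Patients without test-confirmed CDI may enter the cure-rate denominator and could be only partly identified.

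Size and direction cannot be derived from the documents. As an illustration, 10% unconfirmed moves an 89% cure rate to between 83.1% and 90.1%. This rests on three assumptions: that 89% holds in true CDI, that the unconfirmed share is 10%, and that their resolution rate lies between 30% and 100%. Shifts toward the lower end would exceed the sampling half-width even at 1,000 CDI patients (1.9 points); those near the upper end would not.

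This is a cheap improvement to a secondary objective. It does not affect the primary safety objective, and it does not show that the cure rate will be wrong.

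**What to change.** 1. In the CDI block of Supplement 3B, add the four-option item already used in Supplement 4A, for the CDI episode that led to FMT. Take it from the chart; no new testing is needed.
2. In section 8.3, keep the all-comers CDI cure rate as the real-world estimate. Beside it, report the rate in patients with symptoms plus a positive test, by test type, as a sensitivity analysis.
3. Use the item as a covariate in delivery-method comparisons.
4. Because the item cannot separate patients who test positive but have diarrhea from another cause, also report cure by the IBS and IBD co-morbidity already collected.

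The cost is one more chart-abstracted field per CDI recipient. Eligibility and care do not change. Collected at baseline, the item is a single entry; recovering it later would mean going back to charts at up to 75 sites.
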